### 3. Study outcomes

#### 3.1. Efficacy outcomes

##### Primary outcomes:

1. Pain Freedom (PF) at 2 hours, defined as the percentage of patients having a reduction of a moderate or severe migraine headache (Grade 2 or 3) at baseline to no headache (Grade 0) at 2 hours after the beginning of the e-TNS session.
2. Most bothersome migraine-associated symptom (MBS) freedom at 2 hours, defined as the percentage of patients with absence, at 2 hours after the beginning of the e-TNS session, of the most bothersome migraine-associated symptom identified at baseline.

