#### 4.2.1. Recruitment phase

Patients contacted during a standard care visit at the headache clinic/research site or from research site database and advertising will be screened during a visit at the investigation site.

Patient will receive the information and consent documents and have to sign these documents before study procedures are initiated. The patient will be given a unique patient identification (screening) number (mentioned in the header of the patient's CRF). Then, the investigator will verify that the patient meets all the inclusion criteria and none of the 13 first exclusion criteria. If this is the case, the patient will be randomized to either the verum or the sham group and a unique randomization number will be allocated to him/her. This randomization number is mentioned on the sealed kit of investigational devices picked by the investigator and is reported in the patient's CRF. Then, the patient will be trained about the practical use of the Cefaly® Abortive Program device (verum or sham) thanks to an oral explanation, a video and an Instruction sheet. The patient will then perform him/herself a first 20-minute e-TNS training test session with a verum or sham training test device (according to the randomization) to check his/her

ability to use the device appropriately and to bear the sensation of neurostimulation, and therefore that the last exclusion criteria is not met.

Screened patient meeting all inclusion criteria and none of the exclusion criteria are included in the trial and will receive a verum or sham Cefaly® Abortive Program device with accessories to be used at home to treat a single migraine attack and the related paper documents (diary and AE reporting form). The investigator will explain to the patient how to fill in these documents.

The patient will complete a paper practice diary (Example diary) for a simulated migraine during the screening visit, to ensure that he/she fully comprehends the procedure. The investigator or study coordinator will then review this Example diary in details with the patient.

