#### 4.2.2. Acute treatment phase

Included patient will be instructed to treat a single qualifying migraine headache within a 2-month period following the screening visit. A migraine headache is a qualifying migraine when all the following criteria are met:

1. The migraine headache severity is moderate or severe (Grade 2 or 3).
2. The migraine headache is associated with at least one of these migraine-associated symptoms: photophobia, phonophobia, nausea, vomiting.
3. The migraine headache started less than four hours ago.
4. No other migraine headache or headache has occurred in the previous 48 hours.
5. The migraine headache is not already resolving on its own i.e. the pain is not already diminishing.
6. No anti-migraine rescue medication has been taken since the beginning of the migraine headache.

In case of qualifying migraine, patient will have to apply the Cefaly® Abortive Program device (verum or sham) for a complete treatment session of 2 hours as soon as the migraine headache is moderate or severe (Grade 2 or 3).

In his/her paper diary, the patient will have to report the following data just before the start of the e-TNS treatment session (baseline data):

- if there is any aura with the qualifying migraine attack
- the headache pain severity on the following scale: 0 = no pain; 1 = mild pain; 2 = moderate pain; 3 = severe pain

---

 if the patient woke up with a migraine, the starting time of the migraine is considered to be at the time of wake-up.

- the migraine-associated symptoms (photophobia, phonophobia, nausea, vomiting) and will specify which associated symptom is the most bothersome symptom (MBS).

Two hours after the beginning of the treatment session, whatever its duration (normally just after removing the device and the electrode if the session ran correctly for 2 hours), the patient will have to report the following data (2-hour data) in his/her diary:

- the headache pain severity on the following scale: 0 = no pain; 1 = mild pain; 2 = moderate pain; 3 = severe pain
- the migraine-associated symptoms (photophobia, phonophobia, nausea, vomiting)

Patients will be instructed NOT to take any anti-migraine rescue medication during the 2-hour treatment session. Medication intake during the 2-hour treatment phase will be considered as a protocol violation.

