### 7.2. Blinding

The investigator and patient will be blinded from whether the allocated devices are verum or sham.

The treatment allocation will be concealed using the following procedure. Verum and sham devices will be programmed by the manufacturer CEFALY Technology. They will be sent to each investigator by blocks with equal number of verum and sham kits of devices. The only indication on the kit of devices will be a unique randomization number. The list of correspondence between allocation (verum or sham) and randomization number (also named as randomization code) will be provided in a sealed envelope to the coordinating investigator. This procedure ensures a blinding from the enrolling investigator as well.

In case of an emergency, identification of a specific blinded investigational device can be revealed without breaking the blind for the remaining devices. In this case, the investigator should contact CEFALY Technology that will provide the required identification details.

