#### 8.2.1. Sample size

The sample size was computed based on the primary outcome, i.e. pain freedom at 2 hours. The sample size should allow detecting a statistically significant difference between the treatment (verum) and control (sham) outcome value with a power of at least 90% and a 5% level of significance.

In the pilot clinical trial, the pain freedom at 2 hours associated with the Cefaly® Abortive Program treatment was 35.4%. Results from previous randomized, sham-controlled trial using a stimulation device (transcranial magnetic stimulator) as acute treatment of migraine reported 22.0% of pain freedom at 2 hours in the sham group (11).

A power analysis showed that a sample of 239 patients per group allows detecting a statistically significant difference between the treatment (35.4%) and control (22.0%) pain freedom at 2 hours with a power of at least 90% and a 5% level of significance.

Taking into account a rate of 20% of patient loss during the study (based on the pilot clinical trial), at least 299 patients should be included in each group. Consequently, 600 patients will be included in the present clinical investigation.

NOTE: The sample size meets the FDA definition of Phase III clinical investigation (according to the FDA, a clinical investigation can be considered as a Phase III clinical study when the number of participants ranges from 300 to 3,000 volunteers who have the disease or condition).

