### 8.2.3. Statistical methods

- All relevant general, safety and efficacy data will be descriptively summarized at each time point.
- Continuous data will be summarized by the number of subjects (N), the arithmetic mean, the standard deviation, the coefficient of variation as a percentage (CV%), the median, the inter-quartile range, the minimum and the maximum value, when appropriate.
- Categorical data will be summarized by absolute (N) and relative (%) frequency tables.
- Where considered as relevant, the study data will also be graphically depicted.
- For each patient, the outcomes will be calculated according to all data available, and if necessary, imputation of missing data will be performed according to the last value carried forward method.
- Unless otherwise stated, all statistical tests will be conducted at the  $\alpha=0.05$  (2-sided) level.
- Comparison between two independent samples (verum and sham group) will be performed using either the Mann-Whitney U test (also called the Mann-Whitney-Wilcoxon (MWW), Wilcoxon rank-sum test, or Wilcoxon-Mann-Whitney test), the Fisher test or the Anova test.

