### 8.2.4. Statistical analysis

#### Efficacy analysis

The efficacy analysis will be executed on a modified intention-to-treat (mITT) basis.

Patient data will be included in the mITT analysis if all the four following conditions are met:

1. The patient treated a qualifying migraine.
2. The patient applied the Cefaly® Abortive Program treatment (verum or sham) during at least 30 minutes\*.
3. The headache pain severity score **AND** the migraine-associated symptom(s) at baseline were reported in the diary.
4. The headache pain severity score **OR** the migraine-associated symptom(s) at 2 hours were reported in the diary.

\*If the patient stopped the 2-hour treatment session after 30 minutes but before its end for any reason, he/she is kept in the modified intention-to-treat (mITT) analysis if all the other conditions are met.

If the patient takes anti-migraine rescue medication between 2 hours and 24 hours after the beginning of the e-TNS treatment session, the headache pain intensity and migraine-associated symptoms presence

can be affected by the medication and the last value carried forward method (2-hour value carried forward method in this case) will be applied for the 24-hour time point headache pain severity and migraine-associated symptoms.

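### No test is named for the two yes/no primary outcomes, and the 90% power claimed at 239 per group holds for an uncorrected test (90.3%) but not for Fisher (88.5%)

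*Combined protocol and SAP*

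**What the plan says.** Section 3.1 defines two primary outcomes, both proportions of patients. Pain freedom at 2 hours is "defined as the percentage of patients having a reduction of a moderate or severe migraine headache (Grade 2 or 3) at baseline" to grade 0. The second is absence at 2 hours of the most bothersome symptom identified at baseline.

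Section 8.2.3 is the only place where tests are named. It says "Comparison between two independent samples (verum and sham group) will be performed using either the Mann-Whitney U test", and the sentence ends with the alternatives "the Fisher test or the Anova test". It sets a two-sided 5% level but links no test to an outcome or a data type. Section 8.2.4 gives the analysis population and the carry-forward rule and names no test.

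Section 8.2.1 states: "A power analysis showed that a sample of 239 patients per group allows detecting a statistically significant difference". The rates are 35.4% and 22.0%, the target is at least 90% power at the 5% level, and neither a test nor a formula is given. With 20% loss this becomes 299 per group and 600 in total.

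Four further passages bear on the remedy:
- The modified intention-to-treat (mITT) rules in 8.2.4 require that "The headache pain severity score AND the migraine-associated symptom(s) at baseline were reported in the diary". Pain grade 2 or 3 is therefore known for every analysed patient.
- Section 4.2.2 places that record before treatment: "the patient will have to report the following data just before the start of the e-TNS treatment session (baseline data").
- Section 4.2.1 places it after randomization and after exposure to the allocated training device: "The patient will then perform him/herself a first 20-minute e-TNS training test session with a verum or sham training test device".
- Section 7.2 says of the devices: "They will be sent to each investigator by blocks with equal number of verum and sham kits of devices".

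**The concern.** A confirmatory trial should fix its primary test before unblinding, and its power statement should refer to that test. Here three tests are offered with no rule for choosing, and section 8.2 makes the sponsor responsible for the analysis. For yes/no data most readers would infer Fisher, but Fisher is more conservative than an uncorrected test and may not deliver the promised power at 239 per group.

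Two things are at stake: whether the power statement is true for the test that will be used, and whether a borderline result could be significant or not depending on a choice the plan leaves open.

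All three listed tests also ignore baseline pain grade, which is already collected. An unadjusted comparison is valid in a randomized trial, so this is a missed gain and not an error.

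**Working it through.** **Inputs.** Verum 35.4%, sham 22.0%, 5% level, target at least 90%, 20% loss (8.2.1); two-sided (8.2.3); 1:1 allocation (section 5).

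**Step 1: reproduce 239.** Two-proportion formula, pooled variance under the null, no continuity correction, with mean rate (0.354 + 0.220)/2 = 0.287:

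n = [1.960 × √(2 × 0.287 × 0.713) + 1.2816 × √(0.354 × 0.646 + 0.220 × 0.780)]² / 0.134²

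= [1.2539 + 0.8108]² / 0.017956 = 237.4, so 238 per group.

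Using the pooled variance under both hypotheses gives 239.5, the unpooled form 234.2, and the arcsine form 236.5. The continuity-corrected form gives 253. The plan's 239 therefore fits a standard uncorrected test and is not an arithmetic error. Loss: 239/0.80 = 298.75, so 299, as stated.

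**Step 2: exact power by test.** All 2×2 tables were enumerated under two binomials at 35.4% and 22.0%, two-sided 5%:

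| Analysed per group | Uncorrected chi-square | Fisher |
|---|---|---|
| 239 | 90.3% | 88.5% |
| 240 (300 less 20%) | 90.4% | 88.7% |
| 250 | 91.5% | 89.9% |
| 251 | 91.6% | 90.0% |
| 300 (no loss) | 95.5% | 94.6% |

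On 0/1 data, Mann-Whitney (tie-corrected) and ANOVA are nearly the same test as uncorrected chi-square, and both give 90.3% at 239. Fisher first reaches 90% at 251, which is 251 − 239 = 12 more evaluable patients per group. With 300 randomized per group, 251 analysed corresponds to a loss of 1 − 251/300 = 16.3%.

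**Step 3: how often the choice decides the result** (239 per group, probability that Fisher and chi-square disagree):

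| True rates | Disagreement |
|---|---|
| 35.4% vs 22% | 1.8% |
| 32% vs 22% | 3.5% |
| 30% vs 22% | 4.0% |
| 22% vs 22% | 1.1% |

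Whenever they disagree, Fisher is the non-significant one. With 53/239 on sham, 72/239 on verum gives p = 0.061 by Fisher and 0.048 by chi-square. One more responder (73/239) gives 0.048 and 0.038.

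**Step 4: type I error from the choice of test.** With both rates at 22% and 239 per group, the rejection rate is 5.0% for chi-square and 3.9% for Fisher. Rejecting if any listed test rejects also has size 5.0%, so for one outcome the choice causes no inflation.

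**Step 5: CMH test by baseline grade** (simulation, 239 per group, overall rates held at 35.4% and 22.0%, 400,000 trials per scenario). The documents give no rates by grade, so the share of severe attacks (30%, 45% or 60%) and the log odds ratio for grade (0 to 1.4) are assumptions.

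| Share severe | log OR 0 | 0.3 | 0.5 | 1.0 | 1.4 |
|---|---|---|---|---|---|
| 30% | 90.3% | 90.3% | 90.5% | 91.2% | 91.9% |
| 45% | 90.2% | 90.4% | 90.6% | 91.5% | 92.5% |
| 60% | 90.2% | 90.4% | 90.6% | 91.5% | 92.8% |

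Against 90.3% unstratified, the change is −0.1 to +2.5 points. Null rejection for CMH was 4.9% to 5.0%. If the benefit differs by grade (45% severe, risk difference 0 to 25 points in severe attacks, 13.4 overall), CMH power is 90.3% to 92.1%.

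**Step 6: adding site strata.** The documents give no site count, so layouts are assumed: 300 randomized per group, 20% random loss, neither site nor grade prognostic, 100,000 trials. Chi-square gives 90.5% and CMH by grade 90.4%. CMH by site and grade gives 89.7% with 10 sites of 30+30 and 88.9% with 20 unpooled sites of 15+15.

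**The case against.** The case against accepts the core figures and disputes their weight and the remedy.

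- *Fisher can be inferred, since it is the only listed test made for proportions.* That is a fair reading, but under it the power statement is wrong. If the 239 came from an uncorrected test, that test is not named. Either way the text needs an edit.
- *The effect is small.* This stands. The gap is 1.5 points, 20% loss is itself an assumption, section 5 makes 600 a minimum, and the planning rates come from a pilot trial and from another device's sham group. It sets the weight of the point but does not make the power statement true for Fisher.
- *Lack of adjustment is not a defect, and CMH goes further than naming a test.* The first part stands. On the second, naming any single test cures the omission. CMH is a preference, and its gain rests on assumed grade effects. Its cost if grade does not matter is about 0.1 point.
- *Grade is recorded after randomization and a training session on the allocated device.* This stands and should be disclosed. The record still precedes the treated session.
- *Nothing here supports the second primary outcome.* This stands for power: the documents give no sham rate for freedom from the most bothersome symptom, so every power figure concerns pain freedom.
- *The type I statement could be read too widely.* It covers only the choice of test for one outcome. It does not address whether both primary outcomes must succeed or either suffices.

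**Conclusion.** The concern holds. No test is assigned to either primary outcome, and the power claim is true for an uncorrected test (90.3% at 239 per group) but not for Fisher (88.5% at 239, 88.7% at 240). These figures are exact and rest only on the plan's own rates and two-sided 5% level.

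The consequence is modest: a 1.5-point shortfall, equal to 12 evaluable patients per group, gone if loss is about 16%. The open choice would change the conclusion in 1.8% of trials at the planning rates and in about 4% if the true rates were 30% and 22%. The plan should be corrected, but the design is not undermined and the sample size need not change.

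**What to change.** In 8.2.3 or 8.2.4, name one two-sided 5% test for both primary outcomes, and in 8.2.1 state the power for that test.

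- **Preferred:** a CMH test stratified by baseline pain grade (2 versus 3), reported with a common risk difference and 95% confidence interval, and Fisher as a sensitivity analysis. Power for pain freedom at 239 per group stays at about 90% (90.2% even if grade is not prognostic). State that grade is recorded after randomization and the training session but before the treated session.
- **Alternative:** Fisher as primary, with power restated as 88.5% at 239 per group and no added enrolment.
- **Optional:** add site strata, which follow the per-site kit blocks. This needs a pooling rule for small sites fixed before unblinding, and can cost about 1 to 2 points of power if site is not prognostic and sites are small.

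The cost is wording in the statistical section. The data are already collected and no patients are added. Stratifying by grade costs about 0.1 point of power if grade turns out not to matter.

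### The primary test of 2-hour pain freedom makes no use of the baseline pain grade that the trial already collects; stratifying on it would gain 0 to about 3 points of power at no cost

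*Combined protocol and SAP*

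**What the plan says.** Section 8.2.3 sets out the between-group analysis in one line: "Comparison between two independent samples (verum and sham group) will be performed using either the Mann-Whitney U test", or alternatively the Fisher test or Anova. It adds "Unless otherwise stated, all statistical tests will be conducted at the" two-sided 0.05 level. Neither 8.2.3 nor 8.2.4 names a covariate, a stratified test or a regression model for either primary outcome.

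Baseline grade is part of the first primary outcome. Section 3.1 counts patients "having a reduction of a moderate or severe migraine headache (Grade 2 or 3) at baseline to no headache (Grade 0" at 2 hours. Under 4.2.2 the patient records "the headache pain severity on the following scale" (0 to 3) just before starting the session, and also specifies "which associated symptom is the most bothersome symptom (MBS". Section 8.2.4 makes the baseline pain score and the baseline associated symptoms conditions for the mITT set. It does not make naming the MBS a condition.

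The sample size in 8.2.1 rests on an unadjusted comparison of two proportions, "with a power of at least 90% and a 5% level of significance". For verum, "the pain freedom at 2 hours associated with the Cefaly® Abortive Program treatment was 35.4"%. For sham, an earlier trial of another device "reported 22.0% of pain freedom at 2 hours in the sham group". Section 7.2 sends kits to each investigator in blocks balanced between verum and sham. Randomization is not stratified by attack severity, and could not be, because the attack comes later.

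**The concern.** A patient who starts at Grade 3 has further to go to reach Grade 0 than one who starts at Grade 2, so grade is a plausible predictor of pain freedom. When a baseline factor predicts a yes/no outcome, a test stratified on it has a smaller error variance than an unadjusted test, and the estimate moves less with chance differences between arms in the share of severe attacks. The factor is already collected and complete in the analysis set, so the plan gives up this precision without saving anything.

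At stake is a modest amount of power in a trial sized close to its target: 600 x 0.80 / 2 = 240 evaluable patients expected per group, against 239 required.

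**Working it through.** **1. Reproduce the plan's figure.** Inputs from 8.2.1 and 8.2.3: 35.4% v 22.0%, two-sided 5%, 90% power. The pooled normal formula is n = [1.960 x sqrt(2 x p x (1 - p)) + 1.282 x sqrt(p1(1 - p1) + p2(1 - p2))]^2 / (p1 - p2)^2, with p = 0.287. It gives 237.4, so 238 per group. The plan's 239 reproduces within rounding, and power at 239 is 90.2%. Dividing by 0.80 for 20% loss gives 299 per group.

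**2. Power of a listed test.** Fisher is the usual choice among the three for a yes/no outcome. Its exact two-sided power is 88.5% at 239 per group and 88.7% at 240; about 251-254 would be needed for 90%. The gap to the chi-square figure is 90.2 - 88.5 = 1.7 points.

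**3. Power when stratified on grade.** The documents give neither the share of Grade 3 attacks nor the pain-free rate by grade, so both are assumed: 30-50% severe, and a sham rate 0-25 points lower in severe attacks. The overall rates stay at 22.0% and 35.4%, with one odds ratio for treatment in both grades. Simulated power at 239 per group (200,000 trials per setting, simulation error about 0.1 point, no continuity correction):

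| Severe share | Sham rate, moderate / severe | Unadjusted chi-square | Cochran-Mantel-Haenszel |
|---|---|---|---|
| 30-50% | 22% / 22% | 90.2-90.4% | 90.2-90.3% |
| 30% | 25% / 15% | 90.3% | 90.6% |
| 40% | 28% / 13% | 90.3% | 91.3% |
| 40% | 30% / 10% | 90.4% | 92.2% |
| 50% | 34.5% / 9.5% | 90.3% | 93.2% |

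**4. Check one row by formula.** Take 40% severe and sham 30% / 10%. A treatment odds ratio of 2.04 gives verum rates of 46.7% / 18.5%, and 0.6 x 46.7 + 0.4 x 18.5 = 35.4.
- Unadjusted variance: 0.354 x 0.646 + 0.22 x 0.78 = 0.4003.
- Within-grade variance, verum: 0.6 x 0.467 x 0.533 + 0.4 x 0.185 x 0.815 = 0.2097.
- Within-grade variance, sham: 0.6 x 0.30 x 0.70 + 0.4 x 0.10 x 0.90 = 0.1620.
- Ratio: 0.3717 / 0.4003 = 0.929, equivalent to about 239 x 0.071 = 17 patients per group.
- Power, unadjusted: 0.134 / sqrt(0.4003/239) - 1.960 = 1.31, so 90.6% (unpooled variance).
- Power, stratified: 0.134 / sqrt(0.3717/239) - 1.960 = 1.44, so 92.5%.

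The gain of 1.9 points agrees with the simulated 1.8.

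**5. Chance imbalance, same row.** The 95% limit for the difference between arms in the severe share is 1.96 x sqrt(2 x 0.4 x 0.6 / 239) = 8.8 points. The average gap between grades is (20.0 + 28.2) / 2 = 24.1 points. An imbalance at that limit moves the observed difference by 0.088 x 24.1 = 2.1 points, against a planned 13.4.

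**6. Type I error.** In simulation under no treatment effect it is about 5% with and without stratification.

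**The case against.** The strongest reply is that nothing is broken. Randomization balances severity in expectation, the standard error of the unadjusted test already allows for chance imbalance, and the type I error is held at 5%. The planned 239 per group meets 90% by the formula the sponsor evidently used, with the 20% loss built in. This stands. A reader might infer that the main result would be biased, or that the trial is underpowered for want of adjustment. The documents support neither.

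The gain is also assumed. No prognostic effect of grade is given, and with no effect the gain is zero. A 25-point sham gap is a strong effect: at 30% severe it means 29.5% v 4.5%, an odds ratio of about 8.9. Patients are told to treat once pain is moderate or severe, which could make Grade 3 at baseline less common than 30-50%. This stands too, and is why the range starts at zero.

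The baseline is not strictly pre-exposure. It is recorded up to two months after randomization and after a 20-minute training session on a verum or sham device according to allocation (4.2.1). Adjustment therefore assumes that the session does not change the severity of the later attack. The assumption is reasonable but should be written down.

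It is tempting to apply the same argument to MBS freedom. The documents do not support it equally: the mITT conditions require baseline symptoms but not a named MBS, so that stratifier may be incomplete. No sham MBS rate is given, and nothing links symptom type to MBS freedom.

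**Conclusion.** The point holds as one of efficiency for 2-hour pain freedom. The plan lists only unadjusted two-sample tests, although baseline grade is complete in the analysis set. Stratifying on grade would gain 0 to about 3 points of power at 239 per group: 90.2-93.2%, against 90.2-90.4% for an unadjusted chi-square. Against Fisher, about 1.7 points more come from leaving that test's conservatism. That part has nothing to do with grade, but it matters because 88.5% is below the plan's own 90%.

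The figures rest on an assumed severe share of 30-50%, an assumed sham gap of 0-25 points, a common odds ratio and the plan's overall rates. The unadjusted analysis remains valid. For MBS freedom no gain is claimed.

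**What to change.** In 8.2.3 and 8.2.4, before unblinding:

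- Name as the primary test of 2-hour pain freedom a Cochran-Mantel-Haenszel test without continuity correction, stratified by baseline pain grade (2 v 3). Report the Mantel-Haenszel risk difference with its 95% CI.
- Keep the unadjusted test as a sensitivity analysis.
- State the assumption that the training session on the allocated device does not alter the severity of the attack treated later.
- For 2-hour MBS freedom, stratifying by MBS type is optional. If it is adopted, give a rule for patients who record baseline symptoms but name no MBS.

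The cost is wording in the plan only: no new data, visits or patients. If grade proves not to be prognostic, essentially no power is lost.
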